### **8.3 Interim Analyses**

No interim analyses will be conducted.

## **9 RESPONSIBILITIES OF THE INVESTIGATOR**

### **9.1 Good Clinical Practice**

Investigators must adhere to the procedures outlined in this Study Protocol. The procedures set out in this study protocol, pertaining to the conduct, evaluation, and documentation of this study, are designed to ensure that the Investigators and CRO abide by GCP as described in the ICH Guidelines Topic E6: "Guideline for Good Clinical Practice." Compliance with these regulations also constitutes compliance with the ethical principles described in the current revision of the Declaration of Helsinki. The study will also be carried out in keeping with local legal and regulatory requirements.

## **9.2 Ethics**

The appropriate IRB must review the Study Protocol and the Informed Consent Form prior to initiating the study. Any significant modifications to the IRB-approved protocol or informed consent must be made in consultation with the IRB.

## **9.3 Confidentiality of Subjects**

Any information that identifies subjects with respect to this research study will be kept confidential. However, records identifying the subject may be inspected by representatives of the IRB, the Clinical Research Organization (or its designate) if applicable, and/or the FDA. Subjects' identity will remain strictly confidential during all record reviews, as well as in any publication that may result from this research. Subjects will be identified by study code only; their names will not be used.

## **9.4 Informed Consent**

Informed consent is a process that is initiated prior to the individual's agreeing to participate in the study and continuing throughout the individual's study participation. Appropriate discussion of risks and possible benefits of this therapy will be provided to the subjects. Consent forms describing in detail the study interventions/products, study procedures and risks will be given to the subject and written documentation of informed consent is required prior to starting intervention/administration study product. Consent forms will be IRB approved and the subject will be asked to read and review the document. Upon reviewing the document, the investigator will explain the research study to the subject and answer any questions that may arise. The subjects will sign the informed consent document prior to any procedures being done specifically for the study. The subjects should have the opportunity to discuss the study with their surrogates or think about it prior to agreeing to participate. The subjects may withdraw consent at any time throughout the course of the trial. A copy of the informed consent document will be given to the subjects for their records. The rights and welfare of the subjects will be protected by emphasizing to them that the quality of their medical care will not be adversely affected if they decline to participate in this study.

## **9.5 Data Handling and Record Keeping**

Investigators must ensure that proper source documentation for all study activities are diligently maintained and securely kept. Investigators will transfer all relevant data from source documents to the Case Report Form as stipulated in this Study Protocol and his/her signature on the Case Report Form guarantees completeness and integrity of these data. Investigators will maintain reliable study device dispensing/dosing records and will store study supplies in a secure, locked location. In addition, Investigators will ensure that all study-related source documentation and Case Report Forms will be maintained for a period of two years after the conclusion of the study.

## **9.6 Direct Access to Source Data/Documents**

Investigators must ensure that institutional regulations and the Informed Consent Form clearly permit study-related monitoring, audits, IRB review, and regulatory inspections providing direct access to source data and documents.

## **10 SUPPLEMENTS**

- I Wash-Out Periods for Prohibited Medications
- II Study Treatment Application Procedure
- III IGA

**SUPPLEMENT I**  
**Wash-Out Periods for Prohibited Medications**

[figure not shown]
Use of the following medications (concurrent and contraindicated treatments) have either restrictions for usage, or are prohibited during the course of the study and appropriate wash-out periods must be respected:

Medication	Wash-Out Period/Restrictions
Topical Medications on Face 
 
▪ Retinoids
 
▪ Rx Acne Medications (e.g., BPO, antibiotics)
 
▪ OTC Products that contains active ingredients (e.g., BPO washes, BPO lotions, sal acid, etc.)
 
▪ Corticosteroids
 
	14 days prior to Visit 1 14 days prior to Visit 1 7 days prior to Visit 1 14 days prior to Visit 1
Systemic Medications 
 
▪ Antibiotics (indicated for acne vulgaris , no wash out if it is used for sore throat or any other infectious process)
 
▪ Corticosteroids (indicated for acne vulgaris)
 
▪ Antimalarial medications
 
▪ Oral dapsone
 
▪ Retinoids
 
	30 days prior to Visit 1 30 days prior to Visit 1 30 days prior to Visit 1 30 days prior to Visit 1 6 months prior to Visit 1
Isotretinoin	6 months
OTC Acne Products without any active ingredients (e.g. apricot scrubs)	1 Day washout prior to Visit 1
Investigational Drugs	30 Day washout prior to Visit 1
Cosmetic / Surgical Procedures complementary to the treatment of facial acne	2 Weeks

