# 1 GENERAL INFORMATION

## 1.1 Introduction

Acne vulgaris is a chronic disease with devastating sequela of post-inflammatory hyperpigmentation (PIH) in patients with skin of color. The treatment of PIH in acne is complicated and controversial because some treatments such as topical retinoids may cause further PIH due to irritation.

There are several studies evaluating topical retinoids as well as Azelaic acid 15% gel. There is not much information about the effect of benzoyl peroxide and clindamycin combination in acne patients with skin of color except sub-analysis from a community based study with BP 5% and clindamycin combination at AM and a topical retinoid at PM regimen.

Therefore, the use of Onexton Gel as monotherapy in acne patients with only skin of color will be a novel contribution to our knowledge base.

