## 1.2 Study Population

Twenty (20) subjects with skin of color who are 12 years of age or older with moderate facial acne vulgaris and moderate PIH on IGA scale

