# 3 STUDY DESIGN

This is a single-center, open label pilot study. The study is comprised of 5 study visits; Screening, Baseline, and weeks 4, 8, and 16. All subjects will receive Onexton QD at Baseline. We will evaluate Investigator Global Assessment of acne (IGA), total lesion count, inflammatory lesion count, non-inflammatory lesion count, Investigator Global Assessment of PIH and distribution of PIH, adverse events and concomitant medications.

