### **5.3 Concomitant Medication/Treatment**

Any necessary therapies that will not interfere with the response to treatment may be provided at the discretion of the Investigator. The use of any concurrent medication/treatment is to be recorded in the source.

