## **6 ASSESSMENTS OF EFFICACY**

**6.1 Primary Efficacy Variable (Co-Primary endpoints will be the percent of subjects achieving clear or almost clear on IGA scale for acne and PIH at week 16.**

**6.2 Secondary Efficacy Variables: Secondary endpoints will be (1) the percent reduction of inflammatory lesion count at week 16. (2) percent reduction of non-inflammatory lesions at week 16. (3) percent reduction of total lesion count at week 16 (4) the change in PIH distribution at week 16.**

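### Supplement I names no skin-lightening product and no pigment-directed procedure, although PIH clearance at week 16 is a co-primary endpoint

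*Combined protocol and SAP*

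**What the plan says.** Section 6.1 makes the co-primary endpoints "the percent of subjects achieving clear or almost clear on IGA scale for acne and PIH at week 16". Section 6.2 adds change in PIH distribution at week 16 as the fourth secondary endpoint. Section 4.1 requires a PIH score of 3 at entry. Section 1.1 gives the reason for the study as "the use of Onexton Gel as monotherapy in acne patients with only skin of color".

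Supplement I lists the treatments that are restricted or prohibited, with their wash-out periods. Its rows for the face are topical retinoids, prescription acne medications, OTC products with active ingredients, and corticosteroids. Procedures appear in one row, with a 2-week period: "Cosmetic / Surgical Procedures complementary to the treatment of facial acne". No row names a depigmenting or lightening product.

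Exclusion v (Section 4.2) enforces the wash-outs by reference to Supplement I. Exclusion vii concerns skin disorders that could disturb the diagnosis or evaluation of acne; PIH has no counterpart. Section 5.3 adds a general rule: "Any necessary therapies that will not interfere with the response to treatment may be provided at the discretion of the Investigator". It also requires concurrent medication or treatment to be recorded in the source. Section 8.2 analyses all enrolled subjects and has no rule for pigment-directed co-treatment.

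**The concern.** The list of restricted treatments protects the acne endpoint but was not explicitly extended to the PIH endpoint, which has equal standing. A subject could use a prescription lightener, or have a facial procedure for pigmentation, shortly before Visit 1 and still satisfy exclusion v. If such use came to light later, Section 4.3 would not require withdrawal on that ground, because no exclusion criterion mentions it.

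The design cannot absorb this. Section 3 states: "This is a single-center, open label pilot study". All subjects receive Onexton, so there is no comparator in which background pigment treatment would also appear. Any effect of another product on the PIH score or PIH distribution becomes part of the result reported for Onexton. What is at stake is whether those two PIH results can be read as a response to the study gel.

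**Working it through.** The plan gives no sample-size or power figure to reproduce (Section 8.1 states that no formal justification is provided). The check is therefore a reading of the provisions side by side, followed by simple arithmetic.

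**Step 1. Which provisions reach pigment-directed treatment?**

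| Treatment | Before Visit 1 | Visit 1 to week 16 |
|---|---|---|
| Topical retinoids, facial corticosteroids | Covered by Supplement I, no indication stated | Covered by Supplement I |
| OTC lightener with an active ingredient | Ambiguous: open-ended OTC row, but all its examples are acne products | Same ambiguity, plus Section 5.3 |
| Cosmetic lightener that does not fall under the OTC row | Not covered | Section 5.3 only |
| Prescription lightener | Not covered | Section 5.3 only |
| Procedure for facial pigmentation | Not covered: the row is tied to acne treatment | Section 5.3 only |

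Section 5.3 speaks of therapies that are provided at the Investigator's discretion. It is not clear that this reaches something the subject already uses or buys, and it says nothing about use before Visit 1.

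**Step 2. Weight of one subject.** Input from Section 1.2: "Twenty (20) subjects with skin of color who are 12 years of age or older with moderate facial acne vulgaris and moderate PIH on IGA". If all 20 are analysed, one misattributed result moves the PIH percentage by 1/20 = 5 percentage points.

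**Step 3. Direction.** A product used during the study can produce a response that is credited to Onexton (+5 points per subject). A product stopped just before Baseline can lead to a rebound that hides a response (−5 points per subject). The documents do not say which is more likely.

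**Step 4. Illustration with assumed inputs.** Let u be the share of subjects using such products during the study, p the PIH success rate on Onexton alone, and q the success rate among users. The expected upward shift is u × (q − p). The documents give none of these values. Assumed ranges are u = 10% to 30%, p = 20% to 40%, q = 50% to 70%.

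- Smallest: 0.10 × (0.50 − 0.40) = 0.01, or 1 point.
- Largest: 0.30 × (0.70 − 0.20) = 0.15, or 15 points.

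**Step 5. Comparison with sampling error.** Exact (Clopper-Pearson) 95% intervals, starting from an assumed 6 successes of 20:

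| Successes | Rate | 95% interval |
|---|---|---|
| 6/20 | 30% | 11.9% to 54.3% |
| 8/20 (two added) | 40% | 19.1% to 63.9% |
| 10/20 (four added) | 50% | 27.2% to 72.8% |

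The intervals overlap widely, so the data themselves would not reveal a shift of this size.

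**The case against.** The strongest reply is that the plan has more protection than a quick reading of Supplement I suggests.

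- A reader might infer that Supplement I restricts only acne treatments. It does not. Topical retinoids, facial corticosteroids, antimalarials, oral dapsone, systemic retinoids and investigational drugs carry no acne limitation, and Section 1.1 discusses topical retinoids as a treatment for PIH. This part of the reply stands.
- The OTC row for active ingredients is open-ended, and the word acne appears in the separate row for products without active ingredients but not in this one. An OTC lightener may be caught. This stands as an ambiguity; it does not help with prescription products or procedures.
- A reader might infer that subjects are free to use lighteners through week 16. Section 5.3 does not support that: it admits only therapies that will not interfere with the response, and PIH clearance is a response. What remains is that the clause is general, names no pigment product, and leaves self-obtained products unclear.
- Under-reporting of cosmetic products is conjecture. Section 5.3 covers treatments as well as medications, and Section 5.1.1 schedules the question at every visit.
- Monotherapy in Section 1.1 follows a reference to a regimen combined with a retinoid, so it may mean only without a retinoid. The point does not need the wider meaning: the PIH co-primary is still attributed to one product.
- A subject already on a stable lightener enters at grade 3 despite it, so later improvement is not automatically due to that product. This is fair and is one reason why the direction of bias is left open.
- In an uncontrolled pilot, attribution is weak anyway. That is true, but it is no reason to leave open a source of bias that is cheap to close.

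**Conclusion.** The point holds in a limited form. Supplement I does not name depigmenting products, and its procedures row does not extend to procedures for pigmentation, although PIH clearance is co-primary. The gap is clear before Visit 1 for prescription lighteners and pigment-directed procedures. It is ambiguous for OTC lighteners, and during the study it is narrowed but not closed by Section 5.3.

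The only size that follows from the documents is 5 percentage points per misattributed subject, if 20 are analysed. The 1 to 15 point range rests wholly on assumed use and effect and shows only upward shifts. A reader might infer that the PIH result will be inflated by a known amount. The documents do not support that: they give no frequency of use and no effect of such products, and bias can run either way.

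This should be corrected, because it concerns the scope of a rule that protects a co-primary endpoint.

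**What to change.** Reconcile Supplement I and Section 5.3 with the PIH co-primary:

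1. Extend Supplement I to facial depigmenting or skin-lightening products, whether prescription, OTC or cosmetic, and widen the procedures row to include facial hyperpigmentation. Exclusion v then applies without further change. Which products are listed and which intervals apply are clinical decisions for the sponsor.
2. State in Section 5.3 whether the non-interference rule also applies to products that subjects obtain themselves.
3. Under the existing Concomitant Medication/Treatment item, ask specifically about such products and procedures at each visit.
4. In Section 8.2, keep the analysis of all enrolled subjects as the main one, and report the PIH co-primary with and without subjects who used such products or procedures. The version without users is descriptive only, since it removes subjects partly on what they did after enrolment.

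The cost is a short amendment, one added prompt and one sensitivity analysis. The downside is slightly slower screening, because some candidates would have to wash out or would not be enrolled.

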**SUPPLEMENT II**  
**Study Treatment Application Procedure**

[figure not shown]
- Use ONEXTON Gel exactly as your doctor tells you to use it.
- Apply ONEXTON Gel to your face 1 time each day.
- Before you apply ONEXTON Gel, wash your face gently with a mild soap, rinse with warm water, and pat your skin dry.
- To apply ONEXTON Gel to your face, use the pump to dispense 1 pea-sized amount of ONEXTON Gel onto your fingertip (See Figure 1). One pea-sized amount of ONEXTON Gel should be enough to cover your entire face.

Figure 1

- Dot the 1 pea-sized amount of ONEXTON Gel onto six areas of your face (chin, left cheek, right cheek, nose, left forehead, right forehead). See Figure 2.

Figure 2

- After applying the ONEXTON Gel this way, spread the gel over your face and gently rub it in. It is important to spread the gel over your whole face.
- Wash your hands with soap and water after applying ONEXTON Gel.
- If your doctor tells you to put ONEXTON Gel on other areas of your skin with acne, be sure to ask how much you should use.
- Do not use more ONEXTON Gel than prescribed.

### Supplement III

#### Investigator Global Assessment for Acne IGA)

The Investigator will evaluate the IGA using the following scale and **before assessing individual lesions counts:**

Score	Description
0 = Clear Skin	Clear Skin; no inflammatory or non-inflammatory lesions
1 = Almost Clear	Almost clear; rare non-inflammatory lesions with no more than one small inflammatory lesion
2 = Mild Severity	Mild severity; greater than Grade 1; some non-inflammatory lesions with no more than a few inflammatory lesions (papules/pustules only, no nodular lesions)
3 = Moderate Severity	Moderate severity; greater than Grade 2; some to many non-inflammatory lesions and may have some inflammatory lesions, but no more than one small nodular lesion
4 = Severe	Severe; greater than Grade 3; some to many non-inflammatory and inflammatory lesions, but no more than a few nodular lesions
5 = Very Severe	Very Severe; greater than Grade 4; many non-inflammatory and/or inflammatory lesions with some or many nodular lesions

**Supplement IV:**

**Investigator Global Assessment for PIH**

**0 = NONE**

**1 = Slight**

**2 = mild**

**3 = moderate**

**4 = moderately severe**

**5 = severe**

**6 = Very severe**

**Supplement V:**

**0 = No PIH**

**1 = 1% - 10% PIH of the face**

**2 = 11% - 20% PIH of the face**

**3 = 21% - 30% PIH of the face**

**4 = 31% - 40% PIH of the face**

**5 = 41% - 50% PIH of the face**

**6 = More than 50% PIH of the face**

## SUPPLEMENT VI

### FITZPATRICK SKIN TYPE CLASSIFICATION

Skin Type	Description	Examples
I	Always burns easily and severely (painful burn); tans little or none and peels.	People most often with fair skin, blue eyes and freckles; unexposed skin is pale white.
II	Usually burns easily and severely (painful burn); tans minimally or lightly, also peels.	People most often with fair skin, red or blond hair, hazel or even brown eyes; unexposed skin is pale white.
III	Burns moderately and tans about average.	Normal, average Caucasoid; unexposed skin is white.
IV	Burns minimally, tans easily and above average with each exposure; exhibits IPD (immediate pigment darkening) reaction.	People with white or light brown skin, dark eyes (e.g. Mediterranean, Mongoloids, Oriental, Hispanics, etc.); unexposed skin is white or light brown.
V	Rarely burns; tans easily and substantially; always exhibits IPD reaction.	Brown-skinned persons (e.g. Amerindians, East Indians, Hispanics, etc.); unexposed skin is brown.
VI	Never burns and tans profusely; Exhibits IPD reaction.	Black-skinned persons (e.g. African-Americans, Australian and South Indian Aborigines); unexposed skin is black or dark brown.
